9.0 STATISTICAL CONSIDERATIONS

9.1 General Design Issues

This is a phase II, open-label, single arm, PK study to investigate effects of coadministered EFV and RIF on PK of DMPA in HIV- and TB-coinfected women and to evaluate whether the current dosing frequency of DMPA is adequate to suppress ovulation in women when taken together with an EFV- and RIF-containing regimen.

A woman is eligible for this study if she is premenopausal between the ages of 18 and 46 and co-infected with HIV and TB. Women must be on both RIF (600 mg once daily)-containing TB treatment and EFV (600 mg once daily)-based cART at least 4 weeks before study entry.

After HIV- and TB-coinfected women undergo screening evaluations for study eligibility, PK samples for MPA concentrations from eligible women will be taken at study entry. After entry, PK samples for MPA concentrations will be taken every 2 weeks during the 12-week study period. Blood samples for plasma progesterone levels will be collected from all the eligible women for investigating evidence of ovulation during the 12 weeks of DMPA administration.

Eligible women will also undergo study visits for safety labs at weeks 4 and 12. Signs and symptoms will be assessed at bi-weekly study visits.

9.2 Outcome Measures

9.2.1 Primary Outcome Measures

MPA concentration levels obtained at 2, 4, 6, 8, 10, and 12 weeks after DMPA is administered. The 12 week measurement will be the measurement obtained closest to 84 days after DMPA is administered. The allowable window for the measurement is ± 7 days, as stated in section 6.2.3.

Plasma progesterone levels obtained at 2, 4, 6, 8, 10, and 12 weeks after DMPA is administered.

9.2.2 Secondary Outcome Measures

9.2.2.1 Estimation of MPA PK parameters in HIV and TB co-infected women taking EFV and RIF:

MPA PK parameters AUC over the 12 weeks (AUC_{0-12wk}), C_{min} , C_{max} , apparent clearance (CL/F), and half-life ($t_{1/2}$) calculated using standard non-compartmental method: These PK parameters will be calculated based on the MPA concentrations obtained every 2 weeks over the 12 weeks. MPA concentration obtained at entry (prior to DMPA administration) will be evaluated as confirmation that no DMPA was taken prior to study entry.

9.2.2.2 Estimation of time and variability in time to reach MPA 0.1 ng/mL:

Times (weeks) where elimination slopes estimated fitting \log_e -linear regression models to the individual MPA concentrations obtained in the elimination phase reach MPA level of 0.1 ng/mL: The exact sampling time (weeks) will be used.

9.2.2.3 Estimation of the proportion of participants reaching MPA level <0.1 ng/mL at specified time points:

MPA concentration levels obtained at study weeks 6, 8, and 10. Since the week 12 measurements will be evaluated as the primary outcomes (section 9.2.1), the MPA measurements at study weeks 6, 8, and 10 after DMPA administration will be studied for any earlier sign of MPA levels <0.1 ng/mL.

9.2.2.4 Evaluation of toxicity and safety:

All adverse events with toxicity Grade ≥ 3 from signs/symptoms and chemistry and hematology laboratory analyses.

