1.3 Secondary Objectives

- 1.3.1. To estimate the area under the concentration-time curve (AUC), trough concentration (C_{\min}), maximum concentration (C_{\max}), apparent clearance (CL/F), and half-life ($t_{1/2}$) of MPA in HIV and TB coinfecting women taking EFV-based cART and RIF-containing TB treatment.
- 1.3.2. To estimate time and variability in time to MPA C_{\min} reaching 0.1ng/mL or less in HIV and TB coinfecting women taking EFV-based cART and RIF-containing TB treatment.
- 1.3.3. To estimate the proportion of participants who maintain MPA levels above the minimum level thought to suppress ovulation (MPA 0.1ng/mL) through 12 weeks after DMPA administration.
- 1.3.4. To evaluate the toxicity and safety of concurrent RIF, EFV, and DMPA use.

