6.3.5 Clinical Assessments

In addition to the visits specified in section 6.1, the clinical assessments (except height) should be performed when clinically indicated.

Complete Physical Exam

A complete physical examination will be conducted at screening and as part of clinical assessments performed when clinically indicated. The complete physical exam will include, at a minimum, an examination of the skin, head, mouth, and neck; auscultation of the chest; cardiac exam; abdominal exam; examination of the lower extremities for edema; and Karnofsky performance test. It will also include signs and symptoms, diagnoses, and vital signs (weight, height, temperature, pulse, respiration rate, and blood pressure).

Targeted Physical Exam

A targeted physical examination is required at all study visits after screening. The targeted physical exam must include vital signs (temperature, pulse, respiration rate, and blood pressure) and is to be driven by any previously identified or new signs or symptoms including diagnoses that the participant experienced.

Height

Height required to be reported on the CRF at study entry only.

Weight

Weight required at study entry and at all visits.

Waist Circumference

Waist circumference required at study entry and all on-study visits.

Signs and Symptoms

At entry, all grades that occurred 30 days before entry must be recorded in the source document and CRFs.

After entry:

- Grades 1 and 2 toxicities must be recorded in the source document.
- Grades 3 and 4 toxicities must be recorded in both the source document and CRF.
- Record all signs and symptoms that led to a change in treatment regardless of grade on both source document and CRF. Further evaluation will be required for those events that meet Expedited Adverse Event (EAE) or ICH reporting requirements.

Diagnoses

At the entry and post-entry visits, record all diagnoses identified by the ACTG criteria for clinical events and other diseases in the source document and CRFs.

HIV and TB Treatment Modifications

After entry, all modifications to antiretroviral medications and TB drugs including initial doses, subject-initiated, physician modifications and/or protocol-mandated interruptions, modifications, and permanent discontinuation will be recorded on the CRFs.

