6.3.8 Laboratory Evaluations

At screening and entry all laboratory values must be recorded. For post-entry assessments, record all \geq Grade 3 laboratory values. All laboratory toxicities that led to a change in treatment, regardless of grade, must be recorded. Further evaluation will be required for those events that meet EAE or ICH reporting requirements. All protocol required labs will be done at the DAIDS-approved local lab unless otherwise specified.

Hematology

Perform hemoglobin, hematocrit, white blood cell count (WBC), absolute neutrophil count (ANC), and platelets as clinically indicated in addition to the visits specified in section 6.1.

Blood Chemistries

Perform electrolytes (sodium, potassium, chloride, and bicarbonate), creatinine, and blood urea nitrogen as clinically indicated in addition to the visits specified in section 6.1.

Liver Function Tests (LFTs)

Perform total bilirubin, AST (SGOT), and ALT (SGPT), albumin as clinically indicated in addition to the visits specified in section 6.1.

Pregnancy Test

At screening, serum or urine β -HCG (urine test must have a sensitivity of ≤ 25 mIU/mL) may be used.

Urine β -HCG may be used at the entry, post-entry, and premature study discontinuation visits and when clinically indicated.

There must be a negative pregnancy test within 30 days prior to study entry as well as at the time of study entry.

Perform as clinically indicated in addition to the visits specified in section 6.1.

Plasma Progesterone Levels

This will be done at a central lab. For details, please see the LPC found on the A5338 PSWP.

Serum FSH

At screening must be performed on women with LMP >35 days. For details, please see the current laboratory processing chart (LPC) found on the A5338 PSWP.

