9.6.2 Analyses of Secondary Outcome Measurements

9.6.2.1 Estimation of MPA PKs in presence of EFV and RIF:

MPA PK parameters AUC_{0-12wk} , concentration at week 12 (trough concentration, C_{min}), C_{max} , CL/F , and $T_{1/2}$ will be estimated using non-

compartmental approach and descriptive statistics of these PK parameters will be presented. For the purpose of evaluating whether these PK parameters are significantly different from those in women not on the companion drugs, those PK parameters will be compared to those from the historic controls (A5093 Control Arm) using nonparametric two-sample Wilcoxon test. GMRs in MPA PK parameters of co-administration over administration-alone and associated 90% CIs will also be presented to provide magnitude of the differences as a supplementary analysis.

9.6.2.2 Estimation of time and variability in time to reach a MPA 0.1 ng/mL:

Times (weeks) and variability in times to reach MPA 0.1 ng/mL will be estimated using the analysis methods described in section 9.6.1.

9.6.2.3 Estimation of the proportion of participants reaching MPA level <0.1 ng/mL:

The proportion and percentage of participants with MPA concentration levels <0.1 ng/mL will be summarized by each of the study weeks 8 and 10. 90% CI for proportion at each week will be presented using Clopper-Pearson exact method.

9.6.2.4 Evaluation of toxicity and safety:

Signs and symptoms, chemistry and hematology with toxicity Grade ≥ 3 will be tabulated by study week.

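### The safety outcome and its table name only signs/symptoms, chemistry and hematology, so liver tests (on the protocol's own headings), graded diagnoses, pregnancies and an SAE summary have no place in the analysis of objective 1.3.4

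*Protocol*

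**What the plan says.** Secondary objective 1.3.4 is broad: "To evaluate the toxicity and safety of concurrent RIF, EFV, and DMPA use". The outcome that serves it, Protocol 9.2.2.4, is Grade 3 or higher adverse events "from signs/symptoms and chemistry and hematology laboratory analyses". The matching analysis in 9.6.2.4 repeats the list, beginning "Signs and symptoms, chemistry and hematology with toxicity Grade", and specifies one tabulation, by study week.

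The data-collection sections use finer categories. In 6.3.8 the blood chemistry instruction is "Perform electrolytes (sodium, potassium, chloride, and bicarbonate), creatinine, and blood urea nitrogen as clinically indicated", and a separate instruction for liver function tests is "Perform total bilirubin, AST (SGOT), and ALT (SGPT), albumin as clinically indicated". Section 6.3.5 has one heading for signs and symptoms and another for diagnoses, under which sites are to "record all diagnoses identified by the ACTG criteria for clinical events and other diseases". Section 6.3 requires events meeting the ICH seriousness criteria to be recorded, and 7.2 requires a pregnancy outcome form.

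The SAP states that it addresses objectives 1.3.1 and 1.3.2. It contains no safety analysis.

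**The concern.** The outcome is defined by a closed list of sources, and the list is shorter than the set of safety data the study collects. An analyst who follows it literally would produce a safety table without transaminases, bilirubin or any graded diagnosis.

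These are not peripheral here. Section 2.1.2 discusses hepatitis with rifampicin and says it is more frequent with isoniazid, which participants must also take. Section 2.1.1 lists thromboembolic disorders among the less common reactions to DMPA, and such an event would ordinarily be recorded as a diagnosis. Pregnancy bears on the hypothesis in 1.1 that contraceptive efficacy is reduced. Under 7.2 a woman who becomes pregnant has no further PK evaluation. If that happens before week 12, she also drops out of the week-12 MPA proportion, which 9.6.1 bases on women who complete the sampling.

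The by-week format adds a second problem: it counts occurrences at visits and does not say how many women had an event.

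**Working it through.** The plan gives no figure to reproduce, and the point depends on no power or rate calculation. The check compares the categories in which safety data are collected with the sources named in 9.2.2.4 and 9.6.2.4.

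| Category | Where the protocol collects it | Named in 9.2.2.4 and 9.6.2.4? |
|---|---|---|
| Signs and symptoms | 6.3.5; Grades 3 and 4 go on the CRF after entry | Yes |
| Hematology | Own row in 6.1; 6.3.8; weeks 4 and 12 | Yes |
| Chemistry | Own row in 6.1; 6.3.8 (electrolytes, creatinine, urea nitrogen); weeks 4 and 12 | Yes |
| Liver function tests | Own row in 6.1; 6.3.8 (bilirubin, AST, ALT, albumin); weeks 4 and 12 | No, unless chemistry is read generically |
| Diagnoses | Own heading in 6.3.5; 6.3 treats them as gradeable, apart from signs/symptoms and laboratory results | No |
| Pregnancies | Tests in 6.1 at weeks 4 and 12; outcome form in 7.2 | No |
| SAEs | 6.3, by ICH seriousness criteria | Not as a category |

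**Laboratory panels.** Section 6.1 schedules three safety panels after entry: hematology, chemistry and liver function. The outcome names two of the three.

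**Graded classes.** Section 6.3 gives three things to grade: diagnoses, signs and symptoms, and laboratory results. The outcome uses two of the three.

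**SAEs.** Seriousness does not depend on grade or data source. Sections 6.3.5 and 6.3.8 both foresee that a sign, symptom or laboratory event may meet the ICH criteria. An SAE that is also a Grade 3 or higher sign/symptom, chemistry or hematology event is therefore counted. One that is only a diagnosis, is a liver-test event, or is below Grade 3 is not. No table shows SAEs as such.

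**By-week counting.** There are six post-entry visits (weeks 2, 4, 6, 8, 10 and 12), and signs and symptoms are assessed at each. One persistent Grade 3 symptom can fill up to six weekly cells. Chemistry and hematology are scheduled at weeks 4 and 12, so a persistent laboratory abnormality can appear up to twice at scheduled visits. A count of one in each of six weeks could mean one woman or six, and the planned table cannot tell them apart.

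**Can the gap be filled from existing data?** Yes. Section 6.3.8 requires all laboratory values at screening and entry, and all Grade 3 or higher values afterwards. Section 6.3.5 puts all grades of signs and symptoms from the 30 days before entry on the CRF. It also puts diagnoses on the CRF from entry onwards. A comparison with the pre-injection state is therefore possible.

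**The case against.** The best reply is that chemistry is used generically in the statistical chapter. Section 9.1 says only "Eligible women will also undergo study visits for safety labs at weeks 4 and 12", liver tests are drawn at those visits, and 9.6 describes itself as a summary. On that reading the liver omission is loose wording. This is plausible and cannot be excluded, but 6.1 and 6.3.8 define chemistry without liver analytes, and an analyst should not have to guess. Nor does it bring in diagnoses or pregnancies.

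A second reply is that these events are watched during the study. Adverse event reports go to the team, expedited reporting applies, and Letter of Amendment 1 makes two or more pregnancies a trigger for committee review. That is correct, and oversight is not in question. But monitoring does not supply a reported result for objective 1.3.4.

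Third, pregnancy is a weak measure of DMPA when women at risk must use another method, and ovulation is assessed through progesterone as a primary outcome. That is a fair reason not to make pregnancy an efficacy endpoint. It is not a reason to leave it unlisted.

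Fourth, descriptive tabulation is defensible for a secondary objective in a small single-arm PK study. Agreed. The request is for the right rows and a per-woman count, and it does not require formal inference.

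**Conclusion.** The point holds as one about the definition of the outcome and its analysis; data collection and oversight are not at fault. On the protocol's own categories, diagnoses and pregnancies are outside the analysis of 1.3.4. Liver function tests are outside it unless chemistry is meant generically. SAEs have no summary of their own, and the number of women affected is not specified. This assumes that no other analysis document covers 1.3.4; the SAP provided does not.

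The size can be stated only in scope: one of three scheduled safety panels, one of three graded classes, all pregnancies, and some SAEs. The documents give no rate of liver events or diagnoses in this population, so no number of missed events can be stated.

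A reader might infer three stronger things that the documents do not support:

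- **That SAEs are wholly left out.** Those that are Grade 3 or higher signs/symptoms, chemistry or hematology events are counted.
- **That the counted data are the less relevant part.** Most of the common DMPA effects in 2.1.1, such as bleeding, headache, dizziness and abdominal pain, are signs or symptoms and fall within the outcome when Grade 3 or higher.
- **That the AST/ALT eligibility limit in 4.1.9 lets women enter with an abnormality that the table would then count.** That depends on grading cut-offs that the documents cite but do not reproduce.

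The change should be made: an explicit but incomplete list would give an incomplete safety result, and the remedy is cheap.

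**What to change.** Amend 9.2.2.4 and 9.6.2.4, and add objective 1.3.4 to the SAP, as follows:

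1. Name the sources as Grade 3 or higher signs/symptoms, diagnoses, hematology, chemistry and liver function results.
2. List all SAEs, whatever their source or grade, and all pregnancies.
3. Report, overall and by source, the number and percentage of women with at least one post-injection event that is new or worse than the screening or entry value. Each woman is counted once. An exact confidence interval is optional.
4. Keep the by-week table as supportive.

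If liver tests were always meant to fall under chemistry, saying so settles that part. The cost is a few sentences and a few extra table rows. No new data, visits or samples are needed.

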9.2.3 Exploratory Outcome Measures

9.2.3.1 Human genetic variants/polymorphisms that are known to affect PK of EFV (eg, CYP2B6) and RIF (eg, SLCO1B1).

9.2.3.2 Participants' BMIs and body fat percentages collected over the study period of 12 weeks. Body fat percentages will be estimated using age, body weight, height, and waist circumference.

9.3 Randomization and Stratification

Since this study has a single study arm, no randomization will be employed. There will be no stratification for participants.

9.4 Sample Size and Accrual

It is known that DMPA, EFV, and RIF drugs share some common metabolic pathways via the CYP3A4 enzyme system: MPA is metabolized by and induces CYP3A4 activity; RIF is primarily metabolized by CYP2B6 system but also by CYP3A4 and induces CYP3A4 and CYP2B6 enzyme activities; EFV is primarily metabolized by CYP2B6 and both induces and inhibits CYP3A4 enzyme activity (mixed and unpredictable activity). Therefore, it is anticipated that co-administration with EFV and RIF will induce clearance of MPA concentration, resulting in lower MPA concentrations during the elimination phase, compared to those seen when DMPA is administered alone. Thus, DMPA may need to be administered more frequently when used together with EFV and RIF.

The study hypothesis is that concurrent use of EFV and RIF increases the clearance of MPA, resulting in reduced MPA concentrations. The study will evaluate whether more frequent DMPA dosing is needed when DMPA is administered in combination with EFV and RIF in HIV- and TB-infected women. The evaluation of dosing frequency will be conducted by estimating the proportion of women with MPA levels <0.1 ng/mL 12 weeks post-dose (at the end of the dosing cycle). The critical value 0.1 ng/mL for MPA levels was chosen based on published papers including studies by Mishell [17] and Smit et al. [55]. These studies indicate that when MPA level falls below 0.1 ng/mL, serum progesterone level rises and the probability of ovulation increases.

In ACTG DMPA studies A5093 and A5283 in HIV-infected women, of the 79 PK evaluable participants, 5 women had MPA levels <0.1 ng/mL at 12 weeks after a single dose of DMPA was administered. None of these 5 women, however, had any evidence of ovulation (serum progesterone levels remained below 5 ng/mL). In a study by Smit et al. [56] in 94 women, all but one woman had MPA levels above 0.1 ng/mL at 12 weeks after DMPA administration. These 94 women had received either a single dose or multiple doses of DMPA. Therefore, based on the single dose studies, the proportion of women with MPA levels <0.1 ng/mL (sub-therapeutic MPA levels) 12 weeks post-dose is thought to be about 6% in normal DMPA use, although a study conducted by Trussell [57] showed that there is a contraceptive failure rate of about 0.3% when DMPA is used correctly.

The primary analysis outcome will be the proportion of women with sub-therapeutic MPA levels (<0.1 ng/mL) at 12 weeks. A one-sided binomial test with significance level 0.05 will be used to test the null hypothesis that the proportion of women with sub-therapeutic MPA level is 6% or less. A sample size of 42 women provides 90% power to reject the null hypothesis if the proportion of women with sub-therapeutic MPA levels in this study is at least 21% (this is 15% or higher increase from the 6% threshold). With a sample size of 42 women, the underlying true proportion will be declared as statistically significant increase if 6 or more women have sub-therapeutic MPA levels at 12 weeks (this is equivalent to saying that 90% CI for the underlying proportion is entirely above the 6% threshold). Based on the results from a PK study of oral contraceptives containing ethinyl estradiol (estrogen) and norethindrone (progestin) which are metabolized by CYP3A4 enzyme [58], the study team considers that the underlying proportion of women with sub-therapeutic MPA levels of 21% or higher (15% or higher

increase from the 6% threshold) is plausible in the setting of coadministration with EFV and RIF.

The statistical power was also examined to see if the sample size will achieve a plausible power to detect a clinically meaningful decrease (30%) in MPA concentration at 12 weeks (MPA C_{min}) as one of the secondary objectives. With a significance level of 0.05, a one-sided t-test showed about 91% and 84% power to detect a 30% decline when the coefficient of variation (CV) is 60% and 70%, respectively (in the ACTG study A5093, CV of MPA C_{min} was approximately 57% when coadministered with EFV). We note that this power was examined in \log_e -scale since it is known that PK parameter C_{min} has a \log -normal distribution.

To protect against 10% loss of the primary outcomes after study accrual is closed, the study will enroll a total of 46 women. (In the ACTG DMPA study, A5093, the loss of the primary outcomes of week 12 was 9.8% [6 of 61 participants] due to either sample specimen loss or assay results not available.)

A participant is considered to be evaluable for the primary objective if the participant completes the MPA PK sampling during the study period of 12 weeks after DMPA administration. The participant replacement criteria are described in sections 8.1 and 8.2.

The study team anticipates that the study will enroll approximately 4 participants per month and it will take approximately 12 months to meet the target enrollment for the study.

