2.1.1 DMPA

Medroxyprogesterone acetate (MPA, Provera) is a 21-carbon synthetic progestin with high selectivity and activity resembling those of natural progesterone. MPA has been used extensively in combination with estrogens for oral hormone replacement therapy in postmenopausal women. Relative to progesterone, MPA undergoes substantially less first-pass hepatic metabolism when given orally. MPA has a plasma half-life of 24 hours, with hepatic metabolism to various polar compounds and their conjugates [1]. DMPA, given as a 150 mg intramuscular dose, inhibits ovulation for up to 14 weeks and is therefore, given every 3 months to ensure continuous contraception, with a typical use failure rate of 0.3% during the first year [15]. The apparent half-life of DMPA is approximately 50 days after the intramuscular (IM) injection. Peak plasma concentration (1 to 7 ng/mL) is reached within 3 weeks of the injection and decreases exponentially to become undetectable at 120 to 200 days after dosing. MPA levels stay above the concentration needed to suppress ovulation (0.1 ng/mL) for approximately 3 months [16, 17, 18]. MPA levels at 3 months (12 weeks, C_{min}) after injection ranges from 0.04 to 1.31 ng/mL and mean MPA C_{min} is 0.45 ng/mL with coefficient of variation (CV) of 53% when coadministered with NRTIs only and 0.37 ng/mL with CV of 57% when co-administered with EFV-containing regimen. Women may not ovulate for up to 6 months after the last DMPA dosing [19].

DMPA prevents conception by inhibiting gonadotropin release, leading to ovulation suppression and thinning of the endometrial lining. Luteal activity and ovulation, as indicated by a rise in serum progesterone to >5 ng/mL, occurs when the MPA concentration drops to <0.1 ng/mL [17, 20, 21].

DMPA is metabolized via the cytochrome p450 enzyme system [16] and induces the activity of CYP3A4. When given as an injectable, MPA induces activity of CYP3A4 by 25% [18]. PK studies of DMPA with selected antiretroviral agents have not demonstrated a reduced contraceptive efficacy as assessed through ovulation suppression measured by progesterone levels [16, 19]. Non-NRTIs

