(NNRTIs) and protease inhibitors (PIs) have demonstrated significant interactions with combined oral contraceptives (COC), which might lead to decreased efficacy of the COC [22, 23]. Studies of interactions between ART and DMPA have not demonstrated any clinically significant changes in the levels of either selected cARTs or DMPA. Cohn et al. showed that there were similar levels of DMPA in women on selected cART regimens (nelfinavir [NFV], nevirapine [NVP] and EFV) compared to women not on cART [16, 24]. Another small study done recently also failed to show significant changes in the PK of DMPA in HIV-infected women on cART with zidovudine (ZDV), lamivudine (3TC), and EFV [19]. This cART combination did not increase DMPA-related adverse events nor did it decrease the effectiveness of DMPA [19]. DMPA has not been shown to significantly alter the levels of antiretroviral drugs. The levels of EFV remained unchanged compared to baseline in the Cohn et al. study [16]. Current guidelines do not recommend changes in dosing frequency for patients on EFV-containing cART who use DMPA.

It is unknown whether simultaneous treatment of HIV and TB affected the serum concentration, efficacy, or adverse effects (AEs) of DMPA.

There have been concerns about decreased effectiveness of DMPA in obese women. No pregnancies were documented in two large phase 3 trials that included 193 women (of 1787 total) with a body mass index (BMI) of >30 [25]. A detailed study designed to assess the efficacy of DMPA in obese women revealed fluctuating estrogen levels consistent with follicular development, but no evidence of ovulation [26]. Patients being treated for both TB and HIV may experience even more variability in estrogen and DMPA levels. Patients treated for TB typically gain weight. The proportion of fat gain in that setting is variable and may affect DMPA metabolism. In the exploratory objective, BMI and body fat content will be estimated over time and compared to DMPA levels.

Safety Profile:

DMPA is safe in HIV infected women. There were few toxicities in the ACTG A5093 study related to DMPA with abnormal menstrual bleeding being the most frequent and similar to non-HIV-infected populations [16, 24]. Watts et al. demonstrated no significant changes in the levels of circulating HIV viral load in patients after administration of DMPA [24].

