Statistical Analysis Plan

**ACTG A5338: An Open-Label, Non-Randomized Study of
Pharmacokinetic Interactions Among Depot Medroxyprogesterone Acetate
(DMPA), Rifampicin (RIF), and Efavirenz (EFV) in Women Co-Infected
with Human Immunodeficiency Virus (HIV) and Tuberculosis (TB)**

ClinicalTrials.gov Identifier: NCT02412436

**Version 1.0
November 28, 2018**

Introduction

This Statistical Analysis Plan addresses the following secondary objectives listed in the study protocol.

1.3.1. To estimate the area under the concentration-time curve (AUC), trough concentration (C_{\min}), maximum concentration (C_{\max}), apparent clearance (CL/F), and half-life ($t_{1/2}$) of MPA in HIV and TB coinfecting women taking EFV-based cART and RIF-containing TB treatment.

1.3.2. To estimate time and variability in time to MPA C_{\min} reaching 0.1 ng/mL or less in HIV and TB coinfecting women taking EFV-based cART and RIF-containing TB treatment.

Statistical Analysis Plan

- The concentration vs. time data for DMPA will be analyzed using nonlinear mixed-effects (NLME) modelling using the software NONMEM (version 7.4.2) (S. Beal, Sheiner, Boeckmann, & Bauer, 2009) pooling the data from the available studies A5338, A5238 and A5093.
- The modelling approach followed a stepwise procedure to first identify the structural model best describing the data, and then incorporate the effect of the study covariates such as weight, age, and effect of concomitant anti-retroviral and anti-tuberculosis treatment.
- Various structural pharmacokinetic models were evaluated, focusing on correctly characterizing the absorption after intra-muscular injection. The tested models included one and two compartments disposition, with first-order elimination and zero-, first-order, two parallel first order absorption.
- Model selection was based on changes in the NONMEM objective function value (Δ OFV), and visual inspection of conditional weighted residuals (CWRES) versus time, visual predictive checks, and basic goodness of fit plots (GOF).

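### The 91%/84% power in Section 9.4 for a 30% fall in week-12 MPA does not follow from its stated inputs, and the error could run in either direction

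*Protocol*

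**What the plan says.** After the primary calculation, Protocol Section 9.4 tests whether the same sample size can detect a 30% reduction in week-12 MPA (C_min), which it regards as clinically meaningful. It reports that "a one-sided t-test showed about 91% and 84% power to detect a 30% decline when the coefficient of variation (CV) is 60% and 70" per cent. The level is 0.05 and the calculation is on the log_e scale. As support for the CV range it notes that in A5093 the "CV of MPA C_{min} was approximately 57% when coadministered with EFV".

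The section does not say whether the t-test has one sample or two. It gives no reference mean, no control number and no control CV. Earlier in the same section the expected effect is described as "resulting in lower MPA concentrations during the elimination phase, compared to those seen when DMPA is administered alone".

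Section 9.6.2.1 says how the PK parameters will be compared: "those PK parameters will be compared to those from the historic controls (A5093 Control Arm) using nonparametric two-sample Wilcoxon test". It gives no sidedness and no control number, and adds geometric mean ratios with 90% confidence intervals.

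The only A5093 size in the documents is for the whole study: "the loss of the primary outcomes of week 12 was 9.8% [6 of 61 participants". Section 2.1.1 describes "selected cART regimens (nelfinavir [NFV], nevirapine [NVP] and EFV) compared to women not on cART", citing the same two publications that it cites for A5093. It also reports week-12 MPA "with coefficient of variation (CV) of 53% when coadministered with NRTIs only and 0.37 ng/mL with CV of 57" per cent with EFV.

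**The concern.** The power paragraph is offered as evidence that the trial can detect a 30% fall in C_min. A reader who puts the stated sample size, level, scale, effect and CVs into a t-test does not get the stated answer, so at least one input is missing or was coded differently from the text.

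It is also unclear whether the figure belongs to the analysis that will be run. A5338 has a single arm, so any comparison is with either a fixed historical value or historical individual data. Section 9.6.2.1 plans the second, and its power depends on a control count that the protocol does not give. If that comparison turns out non-significant, a reader relying on 91% or 84% could take it as good evidence against a 30% fall when the real power might be lower.

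**Working it through.** **Inputs.** From Section 9.4: n = 42 evaluable (46 enrolled), one-sided 0.05, 30% fall, CV 60% and 70%, log_e scale. From Section 2.1.1: CV 53% for the NRTIs-only group. Control counts are assumptions, because none is given.

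**Conversion to the log scale.** SD = sqrt(ln(1 + CV²)):

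- CV 60%: sqrt(ln 1.36) = 0.5545
- CV 70%: sqrt(ln 1.49) = 0.6315
- CV 53%: sqrt(ln 1.2809) = 0.4976

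The effect of a 30% fall is −ln(0.7) = 0.3567.

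**Step 1: the stated inputs, one sample.** The noncentrality is (effect / SD) × sqrt(n), with 41 degrees of freedom.

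- CV 60%: (0.3567 / 0.5545) × sqrt(42) = 4.17, power 99.3%
- CV 70%: (0.3567 / 0.6315) × sqrt(42) = 3.66, power 97.5%

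The stated pair is not reproduced. Using all 46 enrolled gives 99.6%/98.3%. At n = 42, using the CV directly as the log SD gives 98.4%/94.5%, a raw-scale effect of 0.30/CV gives 93.8%/86.1%, and a two-sided test gives 98.3%/94.7%.

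**Step 2: one sample with the change coded as ln(1.3) = 0.2624.**

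- CV 60%: noncentrality 3.07, power 91.5%
- CV 70%: noncentrality 2.69, power 84.2%

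This matches the stated pair using the protocol's own n, level, scale and CVs. But 0.2624 corresponds to a ratio of 1/1.3 = 0.769, a fall of about 23%.

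**Step 3: two samples, true 30% fall, same CV in both groups.** The noncentrality is 0.3567 / (SD × sqrt(1/42 + 1/m)) with 40 + m degrees of freedom, for m controls.

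| Controls (assumed) | Power, CV 60% | Power, CV 70% |
|---|---|---|
| 20 | 76% | 66% |
| 30 | 85% | 76% |
| 42 | 89.9% | 82.2% |
| 46 | 91.1% | 83.7% |
| 47 | 91.3% | 84.0% |

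The pair appears at 46 to 47 controls (42 to 43 if all 46 enrolled women are counted).

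**Step 4: is that control number available?** A5093 had 61 − 6 = 55 week-12 results over all groups. A control arm of 46 would leave 55 − 46 = 9 for three cART groups together. This is unlikely but not excluded, since the arm size is not in the documents.

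**Step 5: sensitivity.** If the control CV is fixed at 53% (assuming that the NRTIs-only group is the Control Arm), 20 controls give 80%/77% and 30 give 88%/84%. If the Section 9.6.2.1 test is two-sided at 0.05 with equal CVs, a t-test with 20 controls gives 64%/53% and with 30 gives 76%/64%. In simulation at one-sided 0.05, replacing the t-test by the Wilcoxon test costs about 1 to 4 points.

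**The case against.** The strongest reply is that Section 9.4 never mentions two samples, the Wilcoxon test or the Control Arm, so the link to Section 9.6.2.1 is inferred. The simplest reconstruction is the one-sample calculation with ln(1.3), which needs no control group. On that reading the protocol understates its power for a 30% fall against a fixed reference: 91%/84% stated, 99.3%/97.5% correct. This stands. It is a reconstruction and cannot be proved from the documents, but it fits better than an arm of 46.

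A reader might therefore be tempted to infer from the control-number table that power is overstated and the comparison underpowered. The documents do not support that. The counts of 20 and 30 are illustrations, the control CV is not given for the Control Arm, and with a 53% control CV and 30 controls the shortfall is small. The 53% figure also belongs to women on NRTIs, whereas Section 2.1.1 elsewhere describes the comparators as not on cART, so even that CV is uncertain.

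The harm is limited too. Section 9.6.2.1 reports ratios with 90% confidence intervals, so the precision of the comparison will be visible. The SAP addresses the PK objective (1.3.1) by modelling, "pooling the data from the available studies A5338, A5238 and A5093".

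The reply leaves two things unanswered. On the one-sample reading the figure is still wrong for the effect named. And the comparison that the protocol does plan has no power statement that can be checked.

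**Conclusion.** The point holds as a defect in a secondary calculation. The stated 91%/84% does not follow from the stated inputs, which give 99.3%/97.5%. Of the readings tried with 42 women, two return the pair: an effect coded as ln(1.3), equivalent to a fall of about 23%, or an unstated control group of about 46 to 47 with equal CVs.

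The direction is not established. Against a fixed reference the figure is 8 points too low at CV 60% (99.3 − 91) and 13 to 14 too low at CV 70% (97.5 − 84). For the planned Control Arm comparison it may be too high: with equal CVs and a one-sided test, by 15 and 18 points at 20 controls (91 − 76, 84 − 66) or 6 and 8 points at 30 (91 − 85, 84 − 76). The second set is conditional on assumed counts and is not an estimate of the actual error.

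Nothing here touches the primary sample size. The rule of 6 or more among 42 checks out, with one-sided error 0.038 at 6% and power 90.1% at 21%.

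**What to change.** In Section 9.4, state whether the t-test is one- or two-sample, give the log effect used, and correct the figure to a true 30% fall, −ln(0.7) = 0.357. If a fixed historical mean was the reference, say so.

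Then restate power for the comparison in Section 9.6.2.1: 42 women against the actual number of A5093 Control Arm week-12 values, with a CV given for each group, the Wilcoxon test as planned, and the same sidedness written in both sections.

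The cost is one recalculation and a few sentences, with no extra participants. The SAP already pools A5093 data, so the count and CV should be within the team's reach. The only drawback is that the restated figure may be less favourable.
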